3.6.5	Other Laboratory Evaluations	48
3.6.5.1	Definitions and Derivations	48
3.6.5.2	Presentations	48
3.6.6	Vital Signs	48
3.6.6.1	Definitions and Derivations	48
3.6.6.2	Presentations	48
3.6.7	Electrocardiogram	48
3.6.7.1	Definitions and Derivations	48

STATISTICAL ANALYSIS PLAN D3250R00107 – ed. 2.0

3.6.7.2 3.6.8	Presentations Other Safety Assessments	48 48
4	INTERIM ANALYSIS	48
5	REFERENCES	49
6	APPENDIX	50
6.1	Schedule of Activities	50
6.2	Prednisone Equivalent Doses	55

LIST OF ABBREVIATIONS

Abbreviation or	Definition	
Specialized Term		
CCI	CCI	
AE	Adverse event	
CCI	CCI	
ALP	Alkaline phosphatase	
ALT	Alanine transaminase	
AST	Aspartate transaminase	
ATC	Anatomical Therapeutic Chemical (Classification)	
BD	Bronchodilator	
BMI	Body mass index	
BVX	Blood vessel measurements	
CI	Confidence interval	
COVID-19	Coronavirus disease 2019	
CCI	CCI	
eCRF	Electronic Case Report Form	
CSP	Clinical study protocol	
CSR	Clinical study report	
СТ	Computer tomography	
ECG	Electrocardiogram	
FEV ₁	Forced expiratory volume in 1 second	
FRC	Functional residual capacity	
FRI	Functional Respiratory Imaging	
FVC	Forced vital capacity	
GINA	Global initiative for asthma	
Hb	Hemoglobin	
HRCT	High-resolution computer tomography	

Abbreviation or	Definition
Specialized Term	
ICF	Informed consent form
iVlung	Lung volume
iVaww	Airway wall volume
IPD	Important protocol deviation
ISF	Investigator Site File
MedDRA	Medical Dictionary for Regulatory Activities
OCS	Oral corticosteroids
CCI	CCI
PDAP	Protocol deviation assessment plan
PROs	Patient-reported outcomes
CCI	CCI
SAE	Serious adverse event
SAP	Statistical analysis plan
SD	Standard deviation
siVaw	Specific airway volume
CCI	CCI
SoA	Schedule of Activities
SOC	System Organ Class
TLC	Total lung capacity
WHODrug	World Health Organization Drug Dictionary

AMENDMENT HISTORY

CATEGORY		Description of change	In line with	Rationale
Change refers to:	Date	Description of change	CSP?	Nationale
N/A	12/4/2023	Initial approved SAP	Yes	N/A
List of abbreviations	09/11/2023	New abbreviations added	Yes (v 4.0)	Clarification required
Section 3: Statistical Analysis	09/11/2023	Added information about rounding	Yes (v 4.0)	Clarification required
Section 3.2: Endpoint Analysis	09/11/2023	Changes to endpoints	Yes (v 4.0)	Endpoint changes to CSP v 4.0
Section 3.2.1: Primary Endpoint – Change from Baseline in siVaw Measurements	09/11/2023	Prednisone equivalent added	Yes (v 4.0)	Clarification required
Section 3.6.2: Adverse events	09/11/2023	AEs collection dates specified	Yes (v 4.0)	Clarification required
Section 5: References	09/11/2023	New references added	Yes (v 4.0)	Clarification required
Section 6: Appendix	09/11/2023	New appendix added	Yes (v 4.0)	Clarification required
Section 2.3: General considerations	22/01/2024	Table 2 edited: proposed rank removed; abbreviations added, endpoints with proposed rank >7 removed except con	Yes (v 5.0)	Updated as in CSP
Section 3.2: Endpoint analysis	22/01/2024	Table 3 edited, clarification of some endpoints	Yes (v 5.0)	Clarification required
Section 3.2.1: Primary Endpoint – Change from Baseline (Week 0) to week 13 in airway dynamics, using untrimmed total mucus volume at TLC	22/01/2024	Changes to endpoints	Yes (v 5.0)	Endpoint changes to CSP v 5.0
Section 3.2.1.5: Secondary analysis of primary endpoint	22/01/2024	Mixed model equation added	Yes (v 5.0)	Clarification required

STATISTICAL ANALYSIS PLAN D3250R00107 – ed. 2.0

CATEGORY Change refers to:	Date	Description of change	In line with CSP?	Rationale
Section 3.1.6.1 Disease characteristics. Definitions and derivations	12/02/2024	Imputation rules added	Yes (v 5.0)	Clarification required
Section 3.2.4 Secondary Endpoint 3	13/02/2024	Analysis set removed, except Primary analysis set	Yes (v 5.0)	Population removed to streamline analysis
Section 3.2.5 Tertiary Endpoint 1	13/02/2024	Analysis set removed, except Baseline endpoints analysis set	Yes (v 5.0)	Population removed to streamline analysis
Section 3.2.6 Tertiary Endpoint 2	13/02/2024	Analysis set removed, except Primary analysis set	Yes (v 5.0)	Population removed to streamline analysis
Section 3.2.3 Secondary Endpoint 2	16/02/2024	Analysis set removed, except Baseline endpoints analysis set	Yes (v 5.0)	Population removed to streamline analysis

1 INTRODUCTION

In addition to bronchoconstriction and airway thickening, mucus plugging is common and often persistent in patients with asthma and seen on Computer Tomography (CT) scans of most patients. Eosinophils are the major cell type found in the Charcot-Leyden crystals in mucus plugs of asthmatics. Mucus plugs with eosinophilic inflammation may have a profound effect on pulmonary function and the development of exacerbations, and imaging of bronchial segments and scoring of mucus plugging is a well-accepted research tool in respiratory disease (Oguma et al 2021).

Depletion of eosinophils should lead to a reduction in mucus plugging on imaging and improvement of airway patency and airflow distribution. BURAN is a multicentre, single-group, open-label, Phase 4 study. The BURAN study will investigate the short-term benefits of sustained depletion of airway eosinophils by benralizumab, an anti-IL-5R monoclonal antibody, on airway structure and dynamics using FRI in adults with severe eosinophilic asthma.

The purpose of the Statistical Analysis Plan (SAP) is to describe the planned statistical approaches to address the objectives of BURAN, to support the final Clinical Study Report (CSR). The SAP is based on the BURAN Clinical Study Protocol (CSP) version 5.0, dated 08 January 2024.

2 DATA ANALYSIS CONSIDERATIONS

2.1 Timing of Analyses

The analyses will be performed after the end of study. No interim analyses are planned.

2.2 **Analysis Populations**

The analysis data sets are defined as reported in Table 1.

Population/Analysis Set	Description
Enrolled	All participants who sign the informed consent form
Evaluable	All participants who have completed three doses of study intervention and have baseline and post-benralizumab treatment study evaluation (PROs, CT scans, and spirometry tests) – the evaluable population.
Baseline endpoints analysis set	Participants who have baseline measurements and who have had at least one dose of study intervention. Irrespectively of whether they were discontinued for reasons described in Section 7.1 of the CSP will be included for analyses conducted on the study population who at least started study intervention.
Primary analysis population	The portion of the evaluable population that did not have any acute asthma exacerbation nor lower respiratory tract infection during the study period will be the primary analysis population for the endpoints in this study.
Safety analysis set	The safety analysis set consists of all participants who have received at least one dose of study intervention.

Analysis Data Sets Table 1

PRO Patient Reported Outcomes

2.3 **General Considerations**

In this study, Functional Respiratory Imaging (FRI) will be used to measure changes in airway dynamics. The FRI endpoints are defined in Table 2.

Table 2	Functional Respiratory Imaging Parameters				
Parameter from	Description	Parameter	Anticipated Data Selection		
Ductocol	_	from data	_		

Parameter from Protocol	Description	Parameter from data transfer	Anticipated Data Selection Specifications
Untrimmed total mucus volume at TLC (Primary)	Mucus volume	CCI	
Untrimmed total mucus plugs score at TLC (secondary)	Mucus plugs score		
Total air trapping at FRC (secondary)	Air trapping		
Trimmed distal specific iVaww at TLC(secondary)	Airway wall volume		

Parameter from Protocol	Description	Parameter from data transfer	Anticipated Data Selection Specifications
Trimmed distal specific siVaw at TLC (secondary)	Specific airway volume	CCI	
Trimmed distal specific siVaw at FRC (secondary)	Specific airway volume		
Total iVlung at TLC (secondary)	Lung volume		
Total iVlung at FRC (secondary)	Lung volume		
Ċ			

, FRC Functional residual capacity, TLC Total lung capacity

2.3.1 General Study Level Definitions

2.3.1.1 Study Periods

Each participant will participate in the study for a minimum of 15 weeks and up to 23 weeks from the time when informed consent is obtained through to end of study, inclusive of study follow-up. The following are the sequence and duration of study periods:

- Informed consent and instructions for withholding maintenance and rescue asthma medications for screening (24 hours to 30 days prior to screening)
- Screening Visit (V0)
- Baseline/Visit 1 (V1; Week 0; within 1 to 21 days of screening)
- Visit 2 (V2; Week 4 ± 5 days)
- Visit 3 (V3; Week 8 ± 5 days)

- Visit 4 (V4; Week 13 ± 5 days)
- Follow-up/Visit 5 (V5; 2 weeks [± 7 days] after V4) phone call follow-up

Refer to Appendix 6.1 for further information on the Schedule of Activities (SoA) to be performed throughout the study.

Participants will be discharged from the study after the phone call follow-up is completed. This study will not be extended and there will be no roll-over studies. Refer to Section 6.7 of the CSP for further information on study intervention after the end of the study.

For all the endpoints, baseline measurement is defined as the last measurement before start of study intervention administration.

STATISTICAL ANALYSIS PLAN D3250R00107 - ed. 2.0

CCI

a

^b Participants will be evaluated on their medication status, Aes/SAEs and exacerbation history. Note that all safety parameters will be evaluated from pre-screening after informed consent is received until follow-up phone call/Visit 5 or end of treatment follow-up visit for participants who discontinued early in the study.

§: Screening visit includes **CC**, spirometry (with reversibility test if applicable), ECG, and clinical laboratory testing. See SoA (Appendix 6.1) for further details.

2.3.2 Visit Window

The objectives are defined according to outcome measures at Visit 1 (baseline), Visit 2 (Week 4 ± 5 days), Visit 3 (Week 8 ± 5 days) and Visit 4 (Week 13 ± 5 days).

In case more than one measurement is available for any visit window, the one closest to the target day of the visit will be selected for analysis.

In case more than one measurement on the same day is available, the assessment with the earliest time will be selected for analysis.

Visits may be rescheduled within the visit window established in the SoA (Appendix 6.1). If a visit needs to be rescheduled outside the pre-specified visit window and the participant did not meet any of the conditions specified in Sections 5.5.1, 5.5.2, and 5.5.3 of the CSP, the case should be discussed with the AstraZeneca Study Physician and documented in the Investigator site file (ISF). Extension of the run-in period for a participant for any other reason may only be allowed upon approval of the AstraZeneca Study Physician.

2.3.3 Handling of Unscheduled Visits

Any study assessment which is performed outside the visit window for a scheduled visit will be linked to an unscheduled visit. Data collected during unscheduled post-baseline visits will only be reported in the participant listings and will not be considered for summary tables. When unscheduled data are the last obtained before the first study intervention administration, they will be considered as baseline measurements, and will be included in summary tables.

2.3.4 Multiplicity/Multiple Comparisons

Not applicable.

2.3.5 Handling of Protocol Deviations in Study Analysis

Important protocol deviations (IPDs) are those deviations from the protocol identified by the study team as important and requiring summary in the CSR. Methods for identifying IPDs have been defined in the protocol specification assessment plan (PDAP) prior to study start. Protocol deviations will be reviewed periodically throughout the study and the IPDs will be identified and documented.

IPDs are defined as those deviations from the protocol that are likely to have an impact on the completeness, accuracy, and/or reliability of the data for analysis, or that may impact on a participant's rights, safety or well-being. IPDs in this study will be grouped under one of the following four categories:

- 1 Written informed consent not obtained prior to mandatory study specific procedures, sampling, and analyses.
- 2 Those who developed discontinuation of protocol specified therapy criteria during the study but remained on protocol specified therapy.

- 3 Received concomitant medication defined in the protocol as prohibited.
- 4 Visits or procedures impacted by the Coronavirus disease 2019 (COVID-19) pandemic (eg, missed visits, out of window visits, procedures not done due to the COVID-19 pandemic).

3 STATISTICAL ANALYSIS

This section provides information on definitions, derivation and analysis/data presentation per domain.

All continuous variables, including FRI parameters (Table 2), pre-BD FEV₁, pre-BD FVC, CCI , will be summarized using means, standard deviation (SD) and 95% ranges, or medians and inter-quartile ranges, depending on the distributions of the data. Mean changes from baseline in continuous variables will be reported, including asymptotic 95% confidence interval (CI). Categorical data (eg, CCI

) will be summarized as the number and

percentage among participants with non-missing data. Descriptive statistics will be calculated for the data stratified by gender. Unless otherwise stated, all hypothesis tests are two-sided and all hypothesis tests will be performed at a 5% significance level. Analyses will be carried out for overall participants and subgroups as specified in Section 3.2.1.8. FRI parameters may be log-transformed prior to analysis to reduce skewness.

All report outputs will be produced using SAS® version 9.4 or a later version in a secure and validated environment.

For continuous data, mean, and upper and lower quartiles will be rounded to one additional decimal place compared to the original data. The SD will be rounded to one additional decimal place compared to the original data. Median, minimum and maximum will be displayed with the same accuracy as the original data. For categorical data, percentages will be rounded to one decimal place, percentages will not be shown for 0, decimal places will not be shown for 100%.

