This is an interventional, single group, open-label, uncontrolled, prospective, multicenter clinical trial.

Disclosure Statement: This is a single group treatment study with one arm that has no masking.

Number of Participants:

Enrolled	Estimated 38 participants
Assigned	N/A (single-arm study)
Evaluable participants	Estimated 34 participants
Primary analysis population	Estimated 29 participants

Note: "Enrolled" means a participant's, or their legally acceptable representative's, agreement to participate in a clinical study following completion of the informed consent process. Potential participants who are screened for the purpose of determining eligibility for the study, but are not assigned in the study, are considered "screen failures", unless otherwise specified by the protocol.

Intervention Groups and Duration:

Each participant will be participating in the study for a minimum of 15 weeks (maximum of 23 weeks). Informed consent will be obtained from participants between 24 hours and 30 days prior to screening. Participants will be given instructions on how to adequately withhold their maintenance and rescue asthma medications prior to their screening visit. Once participants are enrolled into the study after screening, there will be a run-in period of 1 to 21 days (3 weeks) before Visit 1 (V1) at which time participants will undergo baseline assessments prior to receiving the first dose of benralizumab. There will be a total of three subcutaneously (SC) administered doses of benralizumab 30 mg given at weeks 0 (V1), 4 (V2), and 8 (V3). Final measurements will be taken at V4 at a minimum of 4 weeks to a maximum of 6 weeks after V3, followed by a 2-week follow-up period.

During the study, dose adjustment and dose interruption of benralizumab will not be permitted. Dosing can only be discontinued due to an AE per the Investigator's clinical judgement or unforeseen circumstances. Treatment rechallenge will not be permitted in this study and any participants who discontinue benralizumab will be considered a study withdrawal (see Section 7.1 for further details on criteria for discontinuation of study intervention).

Data Monitoring Committee: Not applicable

Statistical Methods:

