Statistical methods used for the primary objective and secondary objective 1 will be univariate paired *t*-tests and mixed effects modelling. Scatter plots and correlation calculations will be used to assess the baseline association between all FRI parameters of interest and conventional lung function measures, FEV₁ and FVC, for the secondary objective 2. For secondary objective 2, linear regression models will also be fitted to quantify the baseline relationship between each FRI endpoint of interest and the conventional lung function measures. For secondary objective 3, scatter plots and correlation calculations will be used to assess the association between change from baseline in each FRI parameter and change from baseline in the conventional measures. For secondary objective 3, a linear model for FRI endpoints will also be estimated, both adjusted for FEV₁ and FVC and unadjusted for these measurements. These models will include an indicator variable for week 13 to quantify the change from baseline in FRI endpoints. Additional details and methods for other outcomes are provided in Section 9.4.2.

The sample size estimate required to detect a change from baseline in the primary endpoint (untrimmed total mucus volume at TLC) is 29 participants. This estimate is based on results from another study of a biologic treatment and FRI parameters, with the calculation details and corresponding assumptions enumerated in Section 9.2.

Safety analyses will be performed using the safety analysis set. Safety data will be presented using descriptive statistics unless otherwise specified.

The populations to be analyzed consist of:

- Participants who completed the study per protocol definition and had no exacerbation during the study period (primary analysis population)
- All participants who completed the study per protocol definition
- Participants who completed baseline measurements at Visit 1 and had at least one dose of IP, irrespectively of whether they discontinued for reasons as described in Section 7.1 (the baseline endpoints analysis set).
- Subgroup analyses
 - Mucus plugging status: Participants with or without mucus plugs identified using CT scans (Section 8.1.1.2) taken at Visit 1 (week 0)
 - OCS dependency status: OCS-dependent and Non-OCS-dependent participants as defined by the inclusion criteria #4 (Section 5.1)

[figure not shown]
No interim analyses have been planned for this study.

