9.4.1 General Considerations

All continuous variables (including FRI parameters, pre-BD FEV₁, pre-BD FVC, CCI) will be summarized using means, standard deviations and 95% ranges, or medians and inter-quartile ranges, depending on the distributions of the data. Mean changes from baseline in continuous variables will be reported, including asymptotic 95% confidence intervals and standard errors. Categorical data (e.g., CCI CCI CCI CCI CCI CCI asthma control category) will be summarized as the number and percentage among patients with non-missing data. Descriptive statistics will also be calculated for the data stratified by gender. Unless otherwise stated, all hypothesis tests are two-sided and all hypothesis tests will be performed at a 5% significance level. Analyses will be carried out for overall patients and subgroups as specified in Section 9.4.4. Data may be log-transformed prior to analysis to reduce skewness of FRI parameters.

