3.2.1.4 Primary Analysis of Primary Endpoint

The distribution of mucus at Weeks 0 and Week 13 will be graphically displayed in a boxplot. If there is evidence of skewness, data will be log-transformed prior to analysis.

For the primary objective, the analysis will be a paired t-test to determine if there is a significant difference between the mean of mucus volume at Week 0 versus Week 13, irrespective of participant characteristics. The level of significance will be set at 0.05 and so the average mucus volume at Week 0 will be interpreted as significantly different from the average mucus volume at Week 13 if the p-value of the t-test is less than a significance level of 0.05.

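### Asymptotic 95% confidence intervals for mean changes do not match the paired t-test: about 4% too narrow at n = 29 or 34, more in subgroups, with no effect on the primary test decision

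*SAP*

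**What the plan says.** The interval rule stands in both documents. SAP section 3: "Mean changes from baseline in continuous variables will be reported, including asymptotic 95% confidence interval (CI"). Protocol 9.4.1: "Mean changes from baseline in continuous variables will be reported, including asymptotic 95% confidence intervals and standard errors". Neither gives a formula or names a quantile.

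The same changes are tested by a different rule. For the primary endpoint, SAP 3.2.1.4 says "the analysis will be a paired t-test to determine if there is a significant difference" and adds "The level of significance will be set at 0.05". SAP 3.2.2.4 plans a paired t-test for each secondary imaging endpoint. SAP section 3 adds that "all hypothesis tests are two-sided and all hypothesis tests will be performed at a 5% significance level".

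On size, the Protocol synopsis gives the requirement for the primary endpoint ("untrimmed total mucus volume at TLC) is 29 participants") and, for evaluable participants, "Estimated 34 participants". SAP section 3 carries the analyses into the subgroups of SAP 3.2.1.8 (mucus plugging and OCS dependency) and stratifies descriptive statistics by gender. No subgroup sizes are given.

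The SAP Addendum changes populations, the Visit 4 window, rounding, covariance structure and the handling of skewed mucus volume. It leaves the interval rule alone. Its suppression of results with n below 10 (Addendum 2.7) applies only to linear regression models.

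**The concern.** A two-sided 5% paired t-test and a 95% t interval for the same mean change are one calculation: the interval excludes zero exactly when p < 0.05. An interval built with the normal quantile breaks that link. Because 1.960 is below the t quantile at every finite sample size, the mismatch always runs the same way: the interval is narrower than the one the test implies.

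The interval matters here because the objectives are descriptive and there is no control arm, so the estimate and its interval are much of what readers will take away. Protocol 4.2 also equates a clinically meaningful change with a significant one. An interval that excludes zero beside a non-significant p-value would be awkward to explain. The seven secondary imaging endpoints and the subgroups add further places where this could happen.

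**Working it through.** **Inputs**
- Two-sided level 0.05: SAP section 3 and 3.2.1.4.
- n = 29 (primary analysis population) and n = 34 (evaluable): Protocol synopsis. These are planned numbers. The effect size, SD and power behind 29 are blacked out, so that figure cannot be reproduced, and this check does not need it.
- Normal quantile 1.960: the usual meaning of *asymptotic*, and an assumption because the plan names no quantile.
- Normally distributed within-participant differences: an assumption.
- Subgroup sizes 15, 10 and 5: assumptions that show a range.

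**Formulas**
1. Shortfall in width = 1 − 1.960 / t(0.975, n − 1).
2. Coverage of mean ± 1.960 SE = 1 − 2 × P(T with n − 1 df > 1.960).
3. Interval and test conflict when 1.960 < |t| < t(0.975, n − 1), that is, when the t-test p-value lies between 0.05 and 2 × P(T > 1.960). The upper end equals 1 minus the coverage.

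**Worked at n = 29.** t(0.975, 28) = 2.048, and 1.960 / 2.048 = 0.957, so the interval is 4.3% too narrow. Coverage is 94.0%. The conflict range is p from 0.050 to 0.060.

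| n | Source | t quantile | Too narrow by | Coverage | p range in conflict |
|---|---|---|---|---|---|
| 34 | Protocol | 2.035 | 3.7% | 94.2% | 0.050–0.0585 |
| 29 | Protocol | 2.048 | 4.3% | 94.0% | 0.050–0.060 |
| 15 | assumed | 2.145 | 8.6% | 93.0% | 0.050–0.070 |
| 10 | assumed | 2.262 | 13.4% | 91.8% | 0.050–0.082 |
| 5 | assumed | 2.776 | 29.4% | 87.8% | 0.050–0.122 |

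**How often the two would disagree.** At n = 29 the probability is 6.0% − 5.0% = 1.0% if there is no change. From the noncentral t distribution it is at most about 3.4% for any true effect, with the maximum near a standardised mean change of 0.37. At n = 34 the figures are 0.85% and about 2.9%.

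**A bound for the subgroups.** Any two-way split of 29 leaves one part with at most 14 participants. At n = 14 the t quantile is 2.160, the interval is 9.3% too narrow and coverage is 92.8%. If the planned 29 is met, the smaller half of any two-way subgroup is therefore at least that far off.

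**Scale.** SAP 3.2.1.4 log-transforms skewed mucus volume before the t-test, and Addendum 2.11.3 uses log(x + 1) because values can be zero. SAP section 3 does not say which scale the interval for the mean change uses. A raw-scale interval beside a log-scale test can disagree with it whichever quantile is used.

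**The case against.** The strongest reply is that 1.96 is inferred. The plan says only *asymptotic*, the outputs come from SAS, and standard software gives a t interval by default. The reported intervals may therefore turn out correct despite the wording. That is fair, and it is why the result is stated conditionally. It does not rescue the wording: if t intervals are intended, both documents say something else.

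The second reply is that the effect is small at the documented sample sizes. This stands. A loss of about one percentage point of coverage would rarely be noticed.

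A reader might infer more: that the primary conclusion or its type I error is compromised. The documents do not support that. SAP 3.2.1.4 ties significance to the t-test p-value alone, and the interval rule sits in a general paragraph on summaries. Nor do the figures for n of 15, 10 and 5 describe this trial's subgroups, whose sizes are not given.

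The last reply is that the coverage figures require normal differences, while the plan itself expects skewness. This also stands. With skewed data neither the normal nor the t interval is guaranteed its nominal coverage. The mismatch between interval and test remains, because it depends only on the two quantiles.

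**Conclusion.** Wrong as written, minor severity. If *asymptotic* means a normal quantile, the intervals for mean changes are about 4% too narrow at the planned sizes of 29 and 34, and can exclude zero beside a t-test p-value between 0.05 and about 0.06. The direction is certain under that reading. The coverage figures (94.0% and 94.2%) also need normal differences. The primary test is untouched, so the worst outcome there is an occasional borderline mismatch in presentation. The shortfall grows in the mucus-plug, OCS and gender subgroups. Its size there is unknown, and the coverages of 93.0%, 91.8% and 87.8% illustrate a range only. The unstated scale of the interval is a separate route to the same disagreement and should be closed at the same time.

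**What to change.** In SAP section 3 and Protocol 9.4.1, replace *asymptotic* with *t-based (n − 1 degrees of freedom)* for mean changes from baseline, overall and in every subgroup and gender stratum. Add that the interval is computed on the same scale as the paired t-test and back-transformed if a log or log(x + 1) transformation was used. After log(x + 1), the back-transformed result is a ratio of geometric means of (x + 1), read against 1, and should be labelled so. If the raw mean change is also tabulated, label its interval as not the one that corresponds to the test.

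The multiplier becomes 2.048 at n = 29 and 2.035 at n = 34. Coverage returns to 95% under normality, and the interval on the test's scale excludes no change exactly when p < 0.05. The cost is a short wording change in two documents and slightly wider intervals: 2.048 / 1.960 = 1.045, or 4.5% wider at n = 29. No new data or design change is needed.
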